### **8.2.2 The statistical analysis method**

**Descriptive analysis:** Count data is described by proportion, meterage data is described by mean, standard deviation, maximum, minimum description, median, the 25th and 75th percentile.

**Baseline demographic statistical analysis:** Comparison between groups of count data adopts continuous correction of the  $\chi^2$  test. When a cell theory frequency is exceeding 25% is less than 5, use the Fisher exact test. Comparison between groups of normal distribution meterage data adopts the group t-test (two groups) or variance analysis (multigroup). Comparison between groups adopts the Wilcoxon Rank Sum test.

**Curative effect evaluation:** After the test of homogeneity of variance in each center for the primary endpoint of in-stent LLL, comparison between groups uses covariance analysis of adjustment center and baseline effect, and provides the minimum mean square of dependent variable (LLL), minimum variance between groups and 95% confidence interval. For other curative effect indexes, group comparison of normal distribution meterage data adopts the paired t-test. Group comparison of abnormal distribution meterage data adopts the Wilcoxon Sign Rank test. The method of comparison between groups is the same as a baseline analysis.

**Safety evaluation:** According to the investigational and control group, describe the normal number and proportion pre-procedure, and the abnormal number and proportion post procedure respectively. Use the number and incidence of cases to describe the adverse event, and use the continuous correction of  $\chi^2$  test or the Fisher exact test for this ratio. Meanwhile, describe in detail the relationship between the specific performance, extent of all the adverse events in each group and the stent implantation.

All the statistical analyses will be conducted at the bilateral, 0.05 significant level. Use SAS® 9.13 statistical software for statistical analysis, and EPIDATA 3.0 entry software for data management.

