#### 4.3.2.3 Angiographic Endpoints

- 1) In-segment late lumen loss (LLL) at 9 months post-procedure
- 2) In-stent and in-segment (proximal and distal) minimum lumen diameter (MLD) at 9 months post-procedure
- 3) In-stent and in-segment binary restenosis rate angiographically assessed ( $\geq 50\%$  diameter

stenosis) at 9 months post procedure

4) In-stent and in-segment percent diameter stenosis (% DS) 9 months after procedure.

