### **5.5.1 Baseline Angiography**

Following intracoronary injection of nitroglycerin or isosorbide dinitrate, a baseline angiography of the target vessel must be performed according to the QCA corelab guidelines in at least 2 orthogonal views, presenting the target lesion free of foreshortening or vessel overlap.

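### Section 8.2.2 compares the secondary angiographic endpoints without covariates; for 9-month MLD, adjusting for pre-randomisation core-lab QCA would narrow the interval at almost no cost

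*Combined protocol and SAP*

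**What the plan says.** Under the efficacy heading of section 8.2.2, the primary endpoint gets a covariance analysis: "comparison between groups uses covariance analysis of adjustment center and baseline effect". The covariate behind the baseline term is not named.

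For the remaining efficacy measures the section first states: "For other curative effect indexes, group comparison of normal distribution meterage data adopts the paired t-test", with a signed-rank test as the alternative for non-normal data. It then adds: "The method of comparison between groups is the same as a baseline analysis". The baseline paragraph of the same section supplies that method: "Comparison between groups of normal distribution meterage data adopts the group t-test (two groups) or variance analysis (multigroup"), and then "Comparison between groups adopts the Wilcoxon Rank Sum test", presumably for non-normal data. Neither carries a covariate or a centre term.

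The continuous endpoints affected are in section 4.3.2.3: in-segment LLL, in-stent and in-segment percent diameter stenosis (%DS), and "In-stent and in-segment (proximal and distal) minimum lumen diameter (MLD) at 9 months post-procedure".

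The pre-stent film is mandatory. Section 5.5.1 states that "a baseline angiography of the target vessel must be performed according to the QCA corelab guidelines", and section 4.1 sends every angiogram to the independent core laboratory. Section 5.5.1 comes before randomisation in 5.5.2, and section 7.1 makes angiographic eligibility a condition of being randomised. Section 4.4.2 admits reference diameters from 2.25 to 4.0 mm and up to two target lesions per subject. Section 8.1 sizes the trial on the primary endpoint alone.

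**The concern.** The plan accepts adjustment for centre and baseline on its main angiographic endpoint and drops it, without a reason, for the other endpoints read from the same films. For MLD this matters most. A 9-month MLD reflects how large the vessel was as well as how much lumen was lost, and vessel size is fixed before randomisation. Leaving it in the error term widens the interval for the difference between arms. Section 5.5.2 names no stratification by vessel size, so a chance imbalance between arms also moves the unadjusted MLD estimate. At stake is the precision of secondary results that will be reported beside the primary one. The validity of the tests is not in question.

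**Working it through.** **The plan's own figure.** Section 8.1 uses SD 0.41 mm, margin 0.137 mm, one-sided alpha 0.025 and power 85%. Its formula gives 2 × [(1.960 + 1.036)/(0.137/0.41)]² + 1.960²/4 = 161.8, so 162 per arm; 162/0.75 = 216 enrolled per arm. Both stated figures reproduce. I use 162 evaluable per arm below, counting one lesion per subject.

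**Effect of adjustment.** With correlation ρ between covariate and outcome, ANCOVA multiplies the variance by (1 − ρ²). The interval is therefore narrower by 1 − √(1 − ρ²): 4.6% at ρ = 0.3, 13.4% at 0.5 and 28.6% at 0.7.

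**Inputs for MLD.** From the plan: LLL SD 0.41 mm (section 8.1, the largest value in its Table 3) and the eligibility range 2.25 to 4.0 mm. Assumed, because the plan gives no figure:
- 9-month MLD ≈ 0.9 × reference vessel diameter (RVD) − LLL, with LLL independent of vessel size;
- SD of RVD from 0.30 to 0.505 mm, the upper value being a uniform spread over the eligible range, (4.0 − 2.25)/√12 = 0.505;
- extra residual scatter r of 0 or 0.25 mm;
- the core-lab reading of the pre-stent film includes RVD and MLD (the plan does not list the baseline QCA variables).

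**Correlation.** ρ = √[v/(v + 0.41² + r²)], with v = (0.9 × SD of RVD)². For example, at SD 0.30 and r = 0: v = 0.0729, and ρ = √(0.0729/0.2410) = 0.55.

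The 95% half-width is 1.96 × SD × √(2/162) = 0.2178 × SD, using the total SD for the unadjusted interval and √(0.41² + r²) for the adjusted one.

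| SD of RVD (mm) | r (mm) | ρ | Half-width unadjusted (mm) | Half-width adjusted (mm) | Narrower by |
|---|---|---|---|---|---|
| 0.30 | 0 | 0.55 | 0.107 | 0.089 | 16% |
| 0.40 | 0 | 0.66 | 0.119 | 0.089 | 25% |
| 0.505 | 0 | 0.74 | 0.133 | 0.089 | 33% |
| 0.30 | 0.25 | 0.49 | 0.120 | 0.105 | 13% |
| 0.40 | 0.25 | 0.60 | 0.131 | 0.105 | 20% |
| 0.505 | 0.25 | 0.69 | 0.144 | 0.105 | 27% |

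**Chance imbalance.** Under the same assumptions, the 95% range for the between-arm difference in mean RVD is ±0.2178 × 0.30 = ±0.065 mm to ±0.2178 × 0.505 = ±0.110 mm. Multiplied by 0.9, that puts about ±0.06 to ±0.10 mm into the unadjusted MLD difference. The unadjusted interval already allows for this; adjustment removes it.

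**The other endpoints.** In-segment LLL is a within-lesion change. If it is independent of vessel size, ρ = 0 and nothing is gained; ρ of 0.1 to 0.3 would narrow the interval by 0.5% to 4.6%. %DS is already scaled to the reference diameter, and the documents give nothing from which to compute a gain.

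**The case against.** **The text is not wholly clear.** The paired-test sentence comes immediately before the one relied on here. Read as a within-arm comparison, it leaves the between-arm method as described. Read as a between-arm test, it would be wrong for independent groups. The within-arm reading is an inference, but neither reading adds a covariate, so the point stands.

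**The impact is small.** The unadjusted tests keep their error rate under randomisation, and chance imbalance is already reflected in their intervals. The plan states no hypothesis, target difference or success rule for these endpoints. Much of the size-corrected in-stent comparison is already delivered by the adjusted primary LLL. All of this stands, and it makes the point one of efficiency.

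**Stronger readings that the documents do not support.** A reader might infer that precision is lost to vessel size on all the secondary angiographic endpoints alike. It is not: %DS and in-segment LLL largely remove vessel size before the test. A reader might also turn the gain into power for a one-third-SD difference. In section 8.1 that quantity is the non-inferiority margin, with a true difference of zero assumed, and it belongs to an endpoint other than MLD. Fixing the effect at one third of the total MLD SD also lets it grow with the assumed vessel spread, from 0.164 mm (0.491/3) to 0.204 mm (0.612/3), which flatters the result. At a fixed 0.137 mm, adjusted power would be about 85% with no extra scatter and about 73% with 0.25 mm. No power claim should rest on this material.

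**The fix needs care.** Copying the primary model is not enough, because its baseline covariate is undefined and some subjects have two lesions. That objection is right and is met in the fix.

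**Conclusion.** The point holds as a minor, nearly free improvement. Section 8.2.2 leaves the between-arm comparison of continuous secondary angiographic endpoints unadjusted although suitable pre-randomisation films are mandatory and read centrally. The material gain is for in-stent and in-segment MLD, where the interval would be about 13% to 33% narrower (ρ about 0.49 to 0.74). That range rests on the assumed RVD spread, the 0.9 multiplier, independence of LLL from vessel size, and scatter of 0 to 0.25 mm; only the 0.41 mm SD and the eligibility limits come from the plan. For in-segment LLL expect about 0% to 5% for correlations up to 0.3. For %DS the gain is unknown, and consistency is the only argument. The primary conclusion and the sample size are unaffected.

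**What to change.** In section 8.2.2, specify that 9-month in-stent and in-segment MLD and, for consistency, %DS and in-segment LLL are compared by ANCOVA with treatment, centre and named core-lab covariates from the pre-randomisation film. These would be reference vessel diameter for all, plus baseline MLD for the MLD endpoints and baseline %DS for the %DS endpoints. Do not use post-stent values: the stent is implanted after randomisation, so those values can be affected by the assigned device. Report the adjusted mean difference with its 95% interval, and keep the unadjusted t-test or rank-sum test as a supporting analysis.

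In the same edit, state whether the unit is the lesion or the subject and allow for within-subject correlation where a subject has two target lesions; name the baseline covariate in the primary model; and say that the paired and signed-rank tests are for within-arm change, if that is what is meant.

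The cost is a few sentences of analysis text, settled before outcome data are seen. No subjects, visits or films are added.

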## 1 SYNOPSIS

Study Title	BIOTRONIK Orsiro Pre-Marketing Registration Clinical Investigation
Study Objective	To evaluate the effectiveness and safety of the BIOTRONIK Orsiro Sirolimus Eluting Stent (SES) with respect to in-stent Late Lumen Loss (LLL) in a non-inferiority study on de novo coronary lesions at 9 months.
Study Design	The clinical investigation is a non-inferiority, multicenter, blinding evaluation, randomized, parallel controlled clinical study enrolling up to 440 subjects. All subjects will be randomized 1:1 to receive the BIOTRONIK Orsiro SES or the Abbott Xience Prime™ EES, in order to evaluate the efficacy and safety of the SES drug eluting stent in the treatment of coronary artery disease. Clinical follow up visits will take place at 1, 6, 12, 24, 36, 48 and 60 months post procedure. At 9 months (+ 30 days) all subjects will undergo a standard quantitative coronary angiography (QCA) follow up to assess the in-stent LLL as the main efficacious evaluation. Use the major adverse cardiac event (all-cause death, Q-wave, non-Q wave MI and clinically driven TLR) within one year post procedure as the main safety indicator to evaluate the investigational product's safety. The clinical and angiographic data sorting, calculation and statistical analysis will be conducted by an independent data management center and angiographic core laboratory.
Study Sites Up to 15 sites	Less than 15 sites
Study Population	Subjects with coronary artery disease due to de novo stenotic lesions in native coronary arteries, with a reference vessel diameter $\geq 2.25$ mm and $\leq 4.0$ mm and a lesion lengths $\leq 36$ mm.
Study Device	Investigational devices: BIOTRONIK Orsiro SES  Control devices: Abbott Xience Prime™ EES

Inclusion Criteria -Clinical	
 
1. Subject who can understand the investigation's goal has provided written informed consent, and is willing to comply with the study's follow-up requirements.
 
2. Subject is <math>\geq 18</math> years and <math>\leq 75</math> years old, male or female without pregnant.
 
3. Subject is an acceptable candidate for PCI.
 
4. Subject has clinical evidence of asymptomatic ischemia, stable or unstable angina pectoris or old myocardial infarction.
 
5. Subject has no contraindication for dual anti-platelet therapy treatment.
 

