#### 4.3.2.2 Clinical Endpoints

The following endpoints were followed up at 1, 6, and 12 months post-procedure, and once annually for up to 5 years.

- 1) All-cause death
- 2) Cardiac death
- 3) Myocardial infarction
- 4) MI of the target vessel
- 5) Stent thrombosis
- 6) All serious adverse device effects (SADEs)
- 7) Target Lesion Revascularization, TLR
- 8) Target Vessel Revascularization, TVR
- 9) Target Lesion Failure (TLF), composite of cardiac death, target vessel Q-wave or non-Q wave Myocardial Infarction (MI), Coronary Artery Bypass Grafting (CABG), clinically driven TLR
- 10) Target vessel failure (TVF), composite of cardiac death, target vessel Q-wave or non-Q wave Myocardial Infarction (MI) and clinically driven TVR
- 11) Major adverse cardiac event (all-cause death, Q-wave, non-Q wave MI and clinically driven TLR)

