### 7.2 Subject Study Exit

Investigators should make every effort to ensure subjects complete all protocol-required procedures, including study follow-up visits. However, subjects may be required to exit the study, despite an investigator's best efforts. Good Clinical Practice (GCP) guidelines describe the need for clear subject exit procedures, to include when and how to exit subjects from the study, as well as to outline the type and timing of the follow-up and data collection for these subjects.

Subjects may be exited from this study in the following limited situations:

- Subject death
- Subject withdrawal of informed consent
- Investigator believes it is in the best medical interest of the subject to discontinue study participation due to safety reasons
- Subject is considered a screen failure or a procedure failure

In any of the situations noted above, data collected up to and including the exit of the subject will be used in data analysis. No data will be collected after the exit of the subject from the study. Study exits are expected and will be taken into consideration during data analysis as described. Additionally, subject attrition has been calculated into the study sample size. Therefore, all subjects exited from the study will be counted toward the randomization goal and will not be replaced. Investigators must document, in subject medical records, the reasons and circumstances for all subject exits.

---

In cases where further participation in the study poses potential risk to the subject, study exit should

be considered. In addition to subject safety, consideration should be given to the scientific validity of the primary endpoints when making decisions concerning subject exit. Study follow-up options and requirements for subjects exiting from the study should be determined and applied to all subjects exiting for similar reasons. Deviations in subject eligibility, as defined in the protocol, should be considered protocol violations and reported to the Institutional Review Board (IRB) or Ethics Committee (EC) immediately upon discovery, in accordance with local regulations.

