## 8.2 Statistical Analysis

### 8.2.1 The study population is divided into the following categories

- Full analysis set (FAS): The subjects set determined by the intention to treat (ITT) principle refers to the data set constituted by all the subjects participating randomly, using investigational devices and having a baseline curative effect evaluation.
- Per protocol analysis (PPS): Refer to the treatment subpopulation eliminating the serious violation

---

cases.

- Safety analysis set (SS): Refer to the subjects set receiving randomization and minimal one safety evaluation post baseline.

The curative effect evaluation is on the basis of FAS and PPS. All the baseline demographic statistical analysis is on the basis of FAS, and the safety evaluation is on the basis of SS.

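### Section 8.2.2 gives one-year MACE and the five-year clinical endpoints no confidence interval for the arm difference and no rule for incomplete follow-up

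*Combined protocol and SAP*

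**What the plan says.** The synopsis (Study Design) takes MACE (all-cause death, Q-wave or non-Q-wave MI, clinically driven TLR) "within one year post procedure as the main safety indicator to evaluate the investigational product's safety". Section 4.3.2.2 lists eleven clinical endpoints, MACE among them: "The following endpoints were followed up at 1, 6, and 12 months post-procedure, and once annually for up to 5 years".

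Section 8.2.2 does not mention MACE or any other clinical endpoint by name. Two of its paragraphs could cover them:

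- **Safety evaluation:** "Use the number and incidence of cases to describe the adverse event", with a continuity-corrected chi-square or Fisher exact test. Section 8.2.1 adds that "the safety evaluation is on the basis of SS", and defines that set as: "Refer to the subjects set receiving randomization and minimal one safety evaluation post baseline".
- **Curative effect evaluation**, for efficacy measures other than LLL: "The method of comparison between groups is the same as a baseline analysis". For count data, that again means chi-square or Fisher.

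The only interval in section 8.2.2 belongs to the LLL covariance analysis: "minimum variance between groups and 95% confidence interval".

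On early exits, section 7.2 says "data collected up to and including the exit of the subject will be used in data analysis". It also says that the analysis will allow for exits in a way described elsewhere, but section 8 contains no such description. No Kaplan-Meier, log-rank, censoring or person-time method appears anywhere in the document.

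**The concern.** Two things are missing.

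**An interval for the arm difference.** The trial is sized for LLL, not for MACE. If the main safety indicator is reported as two proportions and a p-value, a non-significant result may be read as showing similar safety when the data are still compatible with a material excess on the new stent.

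**A rule for incomplete follow-up.** A 12- or 60-month incidence needs a denominator, and section 8.2.1 defines sets without supplying one. If everyone in the safety set is counted, a subject who leaves without an event contributes as if none occurred later, and the rate is understated. If only subjects with an event or complete follow-up are counted, the rate is overstated. The plan allows either, so the choice could be made after the data are seen. If loss differs between arms, either choice can create a difference that is not real.

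**Working it through.** **Inputs from the document.** Up to 440 subjects randomised 1:1 (synopsis), so 220 per arm. Section 8.1 plans 216 per group, from 162/0.75 = 216, but for LLL only; no rate, margin or power is stated for MACE. Section 2.4 gives a 12-month TLF rate of 6.5% for Orsiro in BIOSCIENCE, used here as a stand-in for MACE.

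**Assumed, because the document gives no figure.** MACE rates of 4-10%, loss of 5-10% at 12 months, a five-year event rate of 15%, and loss of 10-25% at five years. The 25% in section 8.1 is an allowance for the LLL sample size, not a forecast of clinical exits, so it serves only as an upper value.

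**1. Precision of the 12-month MACE difference.** Half-width = 1.96 × √(2p(1−p)/220).

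| Rate in each arm | 95% half-width |
|---|---|
| 4% | 3.7 points |
| 6.5% | 4.6 points |
| 10% | 5.6 points |

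With 216 per arm, the 6.5% row is 4.65 instead of 4.61.

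**2. What the planned output would hide.** Take 20/220 (9.1%) versus 14/220 (6.4%), a difference of 2.7 points. The continuity-corrected chi-square is 0.797, p=0.37. The Newcombe 95% CI is built from the Wilson limits 6.0-13.6% and 3.8-10.4%:

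- lower: 2.73 − √((9.09−5.96)² + (10.40−6.36)²) = −2.4 points
- upper: 2.73 + √((13.62−9.09)² + (6.36−3.83)²) = +7.9 points

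The report would say that there was no significant difference, while an excess of nearly 8 points remained compatible with the data.

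**3. Effect of the denominator.** Assume constant hazards over the period, with event rate p and loss l: λ = −ln(1−p), μ = −ln(1−l).

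- Whole set: observed O = λ/(λ+μ) × (1 − e^−(λ+μ)).
- Event or complete follow-up only: O / (O + e^−(λ+μ)), where e^−(λ+μ) = (1−p)(1−l).

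Worked case, p=15% and l=25% over five years: λ = 0.1625, μ = 0.2877, e^−(λ+μ) = 0.85 × 0.75 = 0.6375. O = (0.1625/0.4502) × 0.3625 = 13.1%. On the other denominator, 0.1309/(0.1309 + 0.6375) = 17.0%.

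| Horizon | True rate | Assumed loss | Whole set | Event or complete follow-up |
|---|---|---|---|---|
| 12 months | 6.5% | 5% | 6.3% | 6.7% |
| 12 months | 6.5% | 10% | 6.2% | 6.8% |
| 5 years | 15% | 10% | 14.3% | 15.7% |
| 5 years | 15% | 25% | 13.1% | 17.0% |

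**4. Unequal loss.** With a true 15% in both arms and the whole-set denominator, loss of 10% versus 15% gives 14.26 − 13.88 = 0.4 points of false difference; 10% versus 25% gives 14.26 − 13.09 = 1.2 points.

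The model treats every event after exit as missed, so the figures in steps 3 and 4 sit at the upper end.

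**The case against.** **Early exits are not stated to be event-free.** A reader might infer from section 8.2.2 that anyone who leaves early is scored as having no event. The document does not say so. Counting the whole safety set is the natural reading, but a denominator of subjects with an event or complete follow-up is not excluded, and it errs upward. Nor would the inference cover every exit: death is both an exit category in section 7.2 and a MACE component, and events before exit are kept. Sections 7.2 and 7.2.1 also maintain contact with subjects who stop without withdrawing consent, seek vital status for those lost, and allow data by phone or from a new provider. The exposure is mainly to non-fatal events after exit. This part of the objection stands.

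**The bias is minor.** At 12 months it is 0.2-0.3 points (6.50 − 6.34 and 6.50 − 6.17) against a half-width of 4.6. At five years, the false difference of 0.4-1.2 points compares with a half-width of about 6.7 points (1.96 × √(2 × 0.15 × 0.85/220)). This stands too, and limits the weight of the denominator argument, particularly for the main safety indicator.

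**Anyone can compute the interval from the counts, and MACE is a secondary endpoint without a hypothesis.** Both are true. But the synopsis gives MACE the leading safety role, and the plan should say what will be reported. That the interval can be derived afterwards does not put it beside the p-value in the report.

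**A full time-to-event programme is more than the defect requires.** Partly accepted: one simple sensitivity analysis is enough.

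**Conclusion.** The point holds in this form: for one-year MACE and the five-year clinical endpoints, the only methods the plan can supply are crude number and incidence with a chi-square or Fisher p-value. No interval is planned for their arm differences, and the handling of exits to which section 7.2 refers is not in section 8. That MACE receives these methods is itself an inference, since section 8.2.2 does not name it, but both routes through the section lead to the same tests.

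The missing interval is the weightier half and does not depend on the denominator. At 220 per arm the data would leave about 4 to 6 points either side of the observed MACE difference, for assumed rates of 4-10%. The missing follow-up rule has a small effect at 12 months. At five years it can move an assumed 15% rate to anywhere from 13.1% to 17.0% at 25% loss. Those event and loss rates are assumptions, and recovery of events after exit would shrink the effect.

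The primary LLL conclusion is not affected. This is an inexpensive improvement that should be made, because it changes what the trial can say about safety.

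**What to change.** In section 8.2.2:

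1. Name one analysis set for the clinical endpoints, including MACE. If the full analysis set is chosen, note that it requires randomisation, device use and a baseline evaluation.
2. Report the 12-month MACE difference between arms with a 95% CI.
3. Estimate the 12-month rate and the annual rates to 60 months by Kaplan-Meier, censored at last contact. Where an endpoint excludes all-cause death, use cumulative incidence with death as a competing event. Give 95% CIs for the arm differences, and have section 7.2 refer to this rule.
4. Report loss to follow-up by arm.

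Add one sensitivity analysis of 12-month MACE, for example applying a range of event rates to lost subjects in each arm, because Kaplan-Meier assumes that loss is unrelated to risk.

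**Cost.** Wording and routine programming; no extra subjects or visits. Event onset dates are source data under section 9.4, and section 7.2.1 uses the last actual contact as the exit date. That section also lets sites enter missed visits instead of an exit, so for those subjects the last-contact date must be derived from visit records.
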